
CRITERIA FOR TREATMENT CONTINUATION
	
Patients will be treated with additional cycles of PM060184 until disease progression (PD), as long as none of the following occur: unacceptable toxicity, and/or patient refusal, and/or Investigators' decision.
 
The administration of subsequent cycles (after Cycle 1) should be delayed if criteria for treatment continuation (Table 2) are not met on the corresponding Day 1. If criteria for treatment continuation are not met on Day 8 (i.e., seven days after the first dose administration of a cycle) (Table 2) of any cycle, administration should be omitted instead of delayed.
 
Table 2. Criteria for treatment continuation.
 
  
 Abnormality	Day 1^a	Day 8	
   
 ANC	≥ 1.5 × 10⁹/L	≥ 1.0 × 10⁹/L	
 
 Platelets	≥ 100 × 10⁹/L	≥ 75 × 10⁹/L	
 
 Hemoglobin^b	≥ 9 g/dL	≥ 9 g/dL	
 
 Total bilirubin	≤ 1.5 × ULN (grade 1)	
 
 AST/ALT	Grade ≤ 1^c	Grade ≤ 2	
 
 Calculated CrCL (Cockcroft-Gault formula)	≥ 40 mL/min	≥ 30 mL/min	
 
 Peripheral sensory/motor neuropathy	Grade ≤ 2	Grade ≤ 2	
 
 Nausea/vomiting, fatigue, anorexia	Grade ≤ 2	Grade ≤ 2	
 
 Other non-hematological drug-related AEs (except metabolic abnormalities^d)	Grade ≤ 1	Grade ≤ 2	
  
 
^a Except Day 1 of Cycle 1.
 
^b If hemoglobin levels are not met, the Investigator will have the option of giving the patient a transfusion instead of delaying (on Day 1) or omitting (on Day 8) a dose.
 
^c Grade ≤ 2, for patients with liver metastases and with AST and/or ALT levels ≤ 5.0 x ULN at registration.
 
^d Any grade accepted for increased GGT. Up to grade 4 accepted for non-symptomatic metabolic abnormalities (e.g., sodium, magnesium, potassium, calcium).
 
AE, adverse event; ALT, alanine aminotransferase; ANC, absolute neutrophil count; AST, aspartate aminotransferase; CrCL, creatinine clearance; GGT, gamma-glutamyltransferase; ULN, upper limit of normal.
 
A maximum delay of 15 days is allowed for the recovery of patients from toxicity. If toxicities have not recovered after this period, the patient should discontinue treatment. Exceptionally, in case of obvious clinical benefit, the patient can remain on
	Abnormality	Day 1 ^a	Day 8	ANC	≥ 1.5 × 10 ⁹ /L	≥ 1.0 × 10 ⁹ /L	Platelets	≥ 100 × 10 ⁹ /L	≥ 75 × 10 ⁹ /L	Hemoglobin ^b	≥ 9 g/dL	≥ 9 g/dL	Total bilirubin	≤ 1.5 × ULN (grade 1)		AST/ALT	Grade ≤ 1 ^c	Grade ≤ 2	Calculated CrCL (Cockcroft-Gault formula)	≥ 40 mL/min	≥ 30 mL/min	Peripheral sensory/motor neuropathy	Grade ≤ 2	Grade ≤ 2	Nausea/vomiting, fatigue, anorexia	Grade ≤ 2	Grade ≤ 2	Other non-hematological drug-related AEs (except metabolic abnormalities ^d)	Grade ≤ 1	Grade ≤ 2

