4.1 INCLUSION CRITERIA

- 1) Voluntarily written informed consent, obtained before the beginning of any study-specific procedures.
- 2) Age \geq 18 years.
- 3) Histologically-cytologically documented adenocarcinoma of colon or rectum that has progressed to the last prior treatment before inclusion.
- 4) Measurable disease according to Response Evaluation Criteria in Solid Tumors (RECIST) v.1.1 (17). If the only tumor lesion is situated in a previously irradiated area or in an area subjected to other loco-regional therapy, progression in the lesion must be demonstrated radiologically.
- 5) Previous treatment in any setting with fluoropyrimidine, oxaliplatin and irinotecan in any combination (unless any is contraindicated).
 - a) Adjuvant chemotherapy-based treatments count as prior therapy, as long as relapse had occurred during or within six months of completion of such therapies.
 - b) Cumulative dose of prior oxaliplatin (if any) must be known.
 - c) Prior cetuximab, panitumumab, bevacizumab, aflibercept, and regorafenib are allowed.
- 6) No more than two prior therapies for metastatic disease.
- 7) Washout periods for prior therapies (defined in relation to planned start of study treatment [first dose administration]):
 - a) At least three weeks since the last administration of an antineoplastic treatment (chemotherapy, biological, targeted or investigational therapies).
 - b) At least three weeks since radiotherapy involving up to 35% of bone marrow (radiotherapy involving $>$ 35% of bone marrow is not allowed) or two weeks since the end of palliative radiotherapy including single doses (18).
 - c) At least four weeks since any major surgical procedure, open biopsy, or significant traumatic injury.
- 8) Eastern Cooperative Oncology Group (ECOG) performance status (PS) 0 or 1 (Appendix 1).
- 9) Life expectancy \geq 3 months.
- 10) Adequate bone marrow, liver, and kidney function:
 - a) Hemoglobin \geq 9 g/dL.
 - b) Absolute neutrophil count (ANC) \geq 1.5×10^9 /L.
 - c) Platelet count \geq 100×10^9 /L.
 - d) Serum creatinine \leq 1.5 mg/dL or calculated creatinine clearance \geq 40 mL/min (Cockcroft-Gault formula, Appendix 2).
 - e) Albumin \geq 2.5 g/dL.
 - f) Total serum bilirubin \leq 1.5 times the upper limit of normal (ULN), except in case of Gilbert syndrome.

g) Alanine aminotransferase (ALT) and aspartate aminotransferase (AST) $\leq 3 \times$ ULN ($\leq 5.0 \times$ ULN in the case of liver metastases).

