5.3 CRITERIA FOR TREATMENT CONTINUATION

Patients will be treated with additional cycles of PM060184 until disease progression (PD), as long as none of the following occur: unacceptable toxicity, and/or patient refusal to receive further study treatment, and/or Investigators’ decision.

The administration of subsequent cycles (after Cycle 1) should be delayed if criteria for treatment continuation ([Table 4](#)) are not met on the corresponding Day 1. If criteria for treatment continuation are not met on Day 8 (i.e. seven days after the first dose administration of a cycle) of any cycle, administration should be omitted instead of delayed.

Table 4. Criteria for treatment continuation.

Abnormality	Day 1 ^a	Day 8
ANC	$\geq 1.5 \times 10^9/L$	$\geq 1.0 \times 10^9/L$
Platelets	$\geq 100 \times 10^9/L$	$\geq 75 \times 10^9/L$
Hemoglobin ^b	≥ 9 g/dL	≥ 9 g/dL
Total bilirubin	$\leq 1.5 \times$ ULN (grade 1)	
AST/ALT	Grade ≤ 1 ^c	Grade ≤ 2
Calculated CrCL (Cockcroft-Gault formula)	≥ 40 mL/min	≥ 30 mL/min
Peripheral sensory/motor neuropathy	Grade ≤ 2	Grade ≤ 2
Nausea/vomiting, fatigue, anorexia	Grade ≤ 2	Grade ≤ 2
Other non-hematological drug-related AEs (except metabolic abnormalities ^d)	Grade ≤ 1	Grade ≤ 2

^a Except Day 1 of Cycle 1.

^b If hemoglobin levels are not met, the Investigator will have the option of giving the patient a transfusion instead of delaying (on Day 1) or omitting (on Day 8) a dose.

^c Grade ≤ 2 , for patients with liver metastases and with AST and/or ALT levels $\leq 5.0 \times$ ULN at registration.

^d Any grade accepted for increased GGT. Up to grade 4 accepted for non-symptomatic metabolic abnormalities (e.g., sodium, magnesium, potassium, calcium).

AE, adverse event; ALT, alanine aminotransferase; ANC, absolute neutrophil count; AST, aspartate aminotransferase; CrCL, creatinine clearance; GGT, gamma-glutamyltransferase; ULN, upper limit of normal.

A maximum delay of 15 days is allowed for the recovery of patients from toxicity. If toxicities have not recovered after this period, the patient should discontinue treatment. Exceptionally, in case of obvious clinical benefit, the patient can remain on treatment but only after discussion and mutual agreement with the Sponsor, and upon recovery of all parameters according to the aforementioned criteria.

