6.3.2 Reasons For Treatment Discontinuation

Patients will receive study treatment while it is considered to be in their best interest or until study termination. Specifically, treatment will continue until:

- Disease progression.
- Unacceptable toxicity (including any toxicity leading to the need for a third dose reduction or severe hypersensitivity reactions, except in the case of obvious clinical benefit, in which event the patient could be allowed to remain on treatment once agreed with the Sponsor).
- Patient refusal to receive further study treatment and/or non-compliance with study requirements.
- Intercurrent serious illness.
- Pregnancy.
- Investigator's decision.
- Protocol deviation with an effect on the risk/benefit ratio of the clinical trial.
- PM060184 treatment delay > 15 days from the due date (except in case of clear clinical benefit and with the Sponsor's approval).
- Clinical cutoff. Patients who have not progressed at these time points could be treated in a compassionate use program (according to country regulations).

Patients who are withdrawn for any reasons must not be re-treated in the context of this study at any time. For follow-up activities, please refer to Section [7.6](#).

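### The Gilbert syndrome exemption from the bilirubin limit at entry is not carried into the treatment-continuation table, so a patient admitted under it can be stopped after one dose without drug toxicity

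*Protocol*

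**What the plan says.** **Entry.** Criterion 10f sets total bilirubin at no more than 1.5 "times the upper limit of normal (ULN), except in case of Gilbert syndrome". The synopsis says the same. Neither gives an alternative ceiling for Gilbert patients, and the syndrome is mentioned nowhere else in the protocol or SAP.

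**Continuation.** The bilirubin row of synopsis Table 2 reads "≤ 1.5 × ULN (grade 1", in a single cell spanning Day 1 and Day 8. Table 4 in Protocol 5.3 has the same row. The only dosing day outside the table is given by footnote a: "Except Day 1 of Cycle 1". Footnote b concerns hemoglobin and transfusion. Footnote c allows a higher AST/ALT grade on Day 1 for patients with liver metastases admitted at up to 5.0 × ULN. Footnote d concerns GGT and metabolic abnormalities. None concerns bilirubin.

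**When the table is not met.** On Day 8, "administration should be omitted instead of delayed". For later Day 1 doses the rule is "The administration of subsequent cycles (after Cycle 1) should be delayed if criteria for treatment continuation" are not met. Then: "A maximum delay of 15 days is allowed for the recovery of patients from toxicity", after which treatment is to stop. Section 5.3 has an exception for obvious clinical benefit with Sponsor agreement, but only "upon recovery of all parameters according to the aforementioned criteria". Section 6.3.2 lists as a stopping reason "PM060184 treatment delay > 15 days from the due date (except in case of clear clinical benefit", with the Sponsor's approval. It does not repeat the recovery condition, and nor does the matching synopsis item.

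**The concern.** The exemption in 10f does something only for Gilbert patients above 1.5 × ULN, and these are the patients whom the continuation table then excludes from further dosing. The protocol admits them knowingly, gives one dose, and withholds the rest for a value that was already present and accepted at entry.

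Footnote c makes this look like an oversight. The transaminase criterion (10g) stands next to the bilirubin criterion (10f) in the entry list. Its allowance was carried into the continuation table and the bilirubin exemption was not, with no reason given for the difference.

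The main stake is the individual patient, who consents and is stopped after one dose without drug toxicity. There is also a smaller effect on the evaluable set behind the 7-of-24 and 25-of-60 rules. Section 6.4 says that, as a general rule, deviations that may affect the risk/benefit evaluation are not authorized. Sites facing the mismatch must stop the patient, deviate, or ask the Sponsor case by case, and may not all do the same.

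**Working it through.** The plan states no figure on this point, so the check is a trace of the rules. Assumption: the patient has Gilbert syndrome, and total bilirubin is above 1.5 × ULN at entry, on each dosing day and throughout any delay.

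| Step | Rule | Result | Doses so far |
|---|---|---|---|
| Registration | 10f, exemption | Eligible | 0 |
| Cycle 1 Day 1 | Footnote a: table does not apply | Dose given | 1 |
| Cycle 1 Day 8 | Bilirubin row not met | Dose omitted | 1 |
| Cycle 2 Day 1 (Day 22) | Bilirubin row not met | Delayed | 1 |
| Day 22 + 15 = Day 37 | Maximum delay reached | Treatment stops | 1 |

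**Do the exceptions help?**
- The exception in 5.3 requires all parameters to meet the table again. Under the assumption, bilirubin does not.
- The exception in 6.3.2 and the synopsis requires clear clinical benefit and Sponsor approval. Day 37 is 36 days after the first dose. The first on-treatment tumor assessment is due at six weeks, 6 × 7 = 42 days. Benefit would have to be judged 42 − 36 = 6 days before the first scheduled scan, after a single dose.
- Neither exception lifts the omission on Day 8.

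**How is the patient counted for PFS3?** Protocol 8.1 and SAP section 4 require a full cycle, or two doses over two cycles. One dose falls short. Stopping for a constitutional value is neither unmanageable toxicity nor a treatment-related AE, so those two routes to evaluability do not apply. Two outcomes remain:
- Progression, deterioration due to the disease, or death from it before the Week 12 evaluation: Protocol 8.1 and SAP section 4 make the patient evaluable as a non-responder. That clause sets no minimum number of doses.
- No such event: the patient has had less than a full cycle and is replaced (Protocol 6.3.4; SAP section 4).

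A one-dose patient can therefore enter the evaluable set only as a failure. Each adds at most one failure to the 24 or the 60.

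**The case against.** **Entry and continuation criteria are different rules and need not match.** Neuropathy must be grade 1 or lower at entry but may be grade 2 later. Creatinine clearance of 40 mL/min is one of the two ways to meet the renal criterion at entry, while 30 is enough on Day 8. This is fair: a difference alone is not an error, and the point is best described as an exemption that was not carried forward. But both of those differences relax the rule after entry. This one tightens it, and only for the patients that the entry rule singled out.

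**A constitutional bilirubin is not a toxicity.** The 15-day rule in 5.3 speaks of recovery from toxicity, so a site could argue that it does not apply. This carries some weight for the stopping rule. It does not carry over to the bilirubin row, which is an absolute threshold not limited to drug-related changes, or to the Day 8 omission. Section 6.3.2 also lists the delay itself as a reason to stop, without reference to toxicity.

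**The trial's counts are protected by replacement.** A reader might infer that every such patient drops out as non-evaluable and is replaced. Protocol 8.1 and SAP section 4 do not support that: patients who progress, deteriorate or die of disease before Week 12 stay in as non-responders. Section 6.3.4 is less clear, because it attaches its progression exception to a missing Week 12 assessment and not to a short treatment course.

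**Nothing in the design changes.** That stands. The hypotheses, alpha, power and decision boundaries do not depend on this point.

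**Conclusion.** The point holds. As written, a Gilbert patient whose bilirubin stays above 1.5 × ULN is eligible, receives one dose and is then stopped by the continuation rules without drug toxicity, unless the Sponsor approves continuation under the clear-benefit wording of 6.3.2. The patient is then replaced or counted as a non-responder, depending on the course of the disease before Week 12.

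Two broader conclusions are tempting and should not be drawn. First, a reader might infer that all Gilbert patients are barred after Cycle 1 Day 1. Those at or below 1.5 × ULN on the dosing day are unaffected, and a patient whose bilirubin falls to the limit within the delay can resume. Second, a reader might apply an outside prevalence of the syndrome to the 60 patients. The documents give no frequency, and prevalence is not the quantity needed: what matters is the share enrolled under the exemption whose bilirubin stays above the limit. The number cannot be estimated from the documents and may be zero.

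The consequence is serious for any patient affected and small for the trial as a whole.

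**What to change.** Reconcile criterion 10f with the bilirubin row so that both state the same position on Gilbert syndrome, in the synopsis (inclusion criteria and Table 2) and in the body (4.1 and Table 4). Which position stands is a clinical decision for the sponsor's medical team.

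The cost is one footnote to the bilirubin row, or one deletion in 10f, made in both places. The SAP sets no bilirubin limit and needs no change.

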4.2 EXCLUSION CRITERIA

- 1) Prior exposure to PM060184.
- 2) Known hypersensitivity to the study drug class or study drug excipient in the formulation.
- 3) Patients with locally advanced disease amenable to local and/or curative therapy (surgery or radiotherapy) at study entry.
- 4) Other serious and/or relevant diseases or clinical situations that, in the opinion of the Investigator, are incompatible with the protocol (including any of the following):
 - a) History of another neoplastic disease (except for basal cell carcinoma of the skin, superficial bladder tumors, or properly treated carcinoma in situ of the uterine cervix or melanoma in situ) unless in remission for at least five years and with no recurrence.
 - b) Symptomatic cerebral and/or leptomeningeal metastasis, spinal cord compression or carcinomatous meningitis.
 - c) Neuropathy of any etiology (other than that caused by previous antineoplastic therapy).
 - d) History of cardiac disease, such as myocardial infarction, in the year prior to registration in the clinical trial; symptomatic/uncontrolled angina pectoris; congestive heart failure or uncontrolled cardiac ischemia; any type of uncontrolled arrhythmia, congenital and/or prolonged QT interval or abnormal LVEF, or uncontrolled arterial hypertension (according to the standards of the World Health Organization [WHO]).
 - e) History of significant psychiatric disease.
 - f) Active infection requiring antibiotic, antifungal or antiviral treatment that, in the opinion of the Investigator, could compromise the patient's capacity to tolerate the therapy.
 - g) Known active liver (hepatitis B or C or cirrhosis) or renal disease.
 - h) Known human immunodeficiency virus (HIV) infection.
 - i) Any other concomitant pathology that could jeopardize the patient's safety or commitment to complete the clinical trial.

- j) Inability or refusal to comply with the protocol or with the clinical trial procedures.
- 5) Pregnancy or lactation.

5. TREATMENT

5.1 STUDY DRUG FORMULATION AND SUPPLY

The drug substance PM060184-CD is a mixture of PM060184 and 2-hydroxypropyl-β-cyclodextrin.

PM060184 drug product (DP) is provided as a sterile lyophilized powder for concentrate for solution for infusion with a strength of 15 mg of the active moiety PM060184.

Before use, PM060184 15-mg vials should be reconstituted with 6 mL of water for injection. The total volume of the reconstituted vial should be diluted with dextrose (5%) up to a total volume of 30 mL to give a PM060184 diluted solution containing 0.5 mg/mL of PM060184. The diluted solution should be protected from exposure to light.

Each 15-mg vial of PM060184 is a single-use vial. The full composition of the reconstituted solution per mL is shown in [Table 3](#).

Table 3. PM060184 vial composition.

Component	Concentration (per mL)	Function
PM060184	2.5 mg/mL	Active moiety
2-Hydroxypropyl-β cyclodextrin (DS 4–5)	200 mg/mL	Solubilizing agent
Water for injection	1 mL	Solvent

DS, degree of substitution.

For instructions regarding drug inventory, handling, reconstitution, dilution, storage and disposal, please refer to the Preparation Guide for infusion for PM060184 and the PM060184 Investigator’s Brochure (IB), both provided as separate documents. Medication preparation records will be kept by the site.

5.2 ADMINISTRATION OF STUDY MEDICATION

PM060184 at a dose of 9.3 mg/m² (dose can be rounded to the first decimal point) will be administered as a 30-minute i.v. infusion via a central or peripheral venous catheter, on Day 1 and Day 8 q3wk (three weeks=one treatment cycle).

5.3 CRITERIA FOR TREATMENT CONTINUATION

Patients will be treated with additional cycles of PM060184 until disease progression (PD), as long as none of the following occur: unacceptable toxicity, and/or patient refusal to receive further study treatment, and/or Investigators’ decision.

The administration of subsequent cycles (after Cycle 1) should be delayed if criteria for treatment continuation ([Table 4](#)) are not met on the corresponding Day 1. If criteria for treatment continuation are not met on Day 8 (i.e. seven days after the first dose administration of a cycle) of any cycle, administration should be omitted instead of delayed.

Table 4. Criteria for treatment continuation.

Abnormality	Day 1 ^a	Day 8
ANC	$\geq 1.5 \times 10^9/L$	$\geq 1.0 \times 10^9/L$
Platelets	$\geq 100 \times 10^9/L$	$\geq 75 \times 10^9/L$
Hemoglobin ^b	≥ 9 g/dL	≥ 9 g/dL
Total bilirubin	$\leq 1.5 \times$ ULN (grade 1)	
AST/ALT	Grade ≤ 1 ^c	Grade ≤ 2
Calculated CrCL (Cockcroft-Gault formula)	≥ 40 mL/min	≥ 30 mL/min
Peripheral sensory/motor neuropathy	Grade ≤ 2	Grade ≤ 2
Nausea/vomiting, fatigue, anorexia	Grade ≤ 2	Grade ≤ 2
Other non-hematological drug-related AEs (except metabolic abnormalities ^d)	Grade ≤ 1	Grade ≤ 2

^a Except Day 1 of Cycle 1.

^b If hemoglobin levels are not met, the Investigator will have the option of giving the patient a transfusion instead of delaying (on Day 1) or omitting (on Day 8) a dose.

^c Grade ≤ 2 , for patients with liver metastases and with AST and/or ALT levels $\leq 5.0 \times$ ULN at registration.

^d Any grade accepted for increased GGT. Up to grade 4 accepted for non-symptomatic metabolic abnormalities (e.g., sodium, magnesium, potassium, calcium).

AE, adverse event; ALT, alanine aminotransferase; ANC, absolute neutrophil count; AST, aspartate aminotransferase; CrCL, creatinine clearance; GGT, gamma-glutamyltransferase; ULN, upper limit of normal.

A maximum delay of 15 days is allowed for the recovery of patients from toxicity. If toxicities have not recovered after this period, the patient should discontinue treatment. Exceptionally, in case of obvious clinical benefit, the patient can remain on treatment but only after discussion and mutual agreement with the Sponsor, and upon recovery of all parameters according to the aforementioned criteria.

5.4 DOSE REDUCTION

Dose can be reduced on the basis of the worst toxicity (drug-related adverse event [AE]) occurring since the previous dose (e.g., Day 1 or Day 8 of any cycle except for Day 1 of Cycle 1). The PM060184 dose reduction schedule is described in [Table 5](#), and criteria according to toxicity in [Table 6](#) and [Table 7](#).

Table 5. PM060184 dose reduction levels.

Dose level	PM060184
-1	7.5 mg/m ²
-2	6.0 mg/m ²

Table 6. Criteria for PM060184 dose reduction for hematological toxicity.

Abnormality	Nadir value	PM060184
ANC	< $0.5 \times 10^9/L$ with fever ($\geq 38.5^\circ C$)/infection, or < $0.5 \times 10^9/L$ for ≥ 3 days	Reduce one dose level
Platelet count	< $50 \times 10^9/L$, with significant bleeding, or < $25 \times 10^9/L$	Reduce one dose level

A second occurrence of the aforementioned toxicities should lead to a further dose reduction (i.e., dose level -2). No more than two dose reductions will be allowed.

ANC, absolute neutrophil count.

Table 7. Criteria for PM060184 dose reduction for non-hematological toxicity.

Abnormality	Worst NCI-CTCAE grade	PM060184
Peripheral sensory/motor neuropathy	≥ 3	Reduce one dose level
Prolonged peripheral sensory/motor neuropathy ^a	≥ 2	Reduce one dose level
Abdominal pain (if reoccurring after the first administration)	≥ 3	Reduce one dose level
Nausea/vomiting despite adequate antiemetic treatment	≥ 3	Reduce one dose level
Fatigue (if reoccurring or persistent after Cycle 2)	≥ 3	Reduce one dose level
Other treatment-related AEs according to the Investigator's criteria	≥ 3	Reduce one dose level

A second occurrence of these toxicities should lead to a further dose reduction (i.e., reduction to dose level -2). No more than two dose reductions will be allowed.

^a Lasting more than two cycles.

AE, adverse event; NCI-CTCAE, National Cancer Institute Common Terminology Criteria for the Classification of Adverse Events.

No more than two dose reductions per patient will be allowed in the course of this clinical trial. Patients requiring more dose reductions should discontinue treatment, except in the event of obvious clinical benefit, in which case, treatment may continue after discussion and mutual agreement with the Sponsor.

No dose escalations will be allowed in this clinical trial.

